1.0 INTRODUCTION – BACKGROUND & RATIONALE

1.1 Significant unmet need in treatments of advanced non-small cell lung cancers

[figure not shown]
Despite the recent success of immune checkpoint inhibitors, only a small proportion of patients with non-small cell lung cancer gain clinical benefit from such therapies. Many patients are either refractory to or relapse after such therapies. Since the FDA approval of PD-1 (programmed death receptor-1) inhibitors (nivolumab, pembrolizumab) in advanced non-small cell lung cancer as single agents or in combination with chemotherapy first-line in metastatic nonsquamous NSCLC (carboplatin, pemetrexed, and pembrolizumab), many patients have been treated with these drugs as a standard of care treatment. However, many of them were found to be refractory to or progressed on such treatments. Moreover, many patients with various types of cancers who had PD-1/PD-L1 inhibitors administered as part of clinical trials are now refractory to such treatments.

Therefore there is high unmet need in non-small cell lung cancer to increase the efficacy of immune checkpoint inhibitors. Also, since most of novel immunotherapy trials, whether in single agent or in combination, exclude patients who have previously been exposed to other forms of immunotherapy including PD-1/PD-L1 inhibitors, these patients have significantly limited access to investigational therapeutics. Therefore, there is substantial unmet need for treatment options for patients with non-small cell lung cancer refractory to PD-1/PD-L1 inhibitors.

1.2 Immune stimulating properties of Metformin:

Metformin is one of the most commonly prescribed medications for the treatment of diabetes mellitus. Experiments in animal models of pancreatic cancer demonstrated anti-tumor properties of metformin via various mechanisms including inhibition of insulin like growth factor-1 (IGF-1) and mTOR, along with activation of AMPK and tuberous sclerosis complex (TSC1, TSC2)¹. Furthermore, epidemiologic data have repeatedly demonstrated decreased cancer incidence and mortality in patients taking metformin ²⁻⁵

Figure 1. Anti-cancer Mechanism of Metformin

NU Study Number: NU 16L04
Other Study Number: CA 209-801

Of note, recent experiments have also suggested that metformin has immune modulatory properties. Metformin inhibited immune exhaustion of CD8+ tumor induced lymphocytes (TIL), thereby enhancing T cell mediated immune response to tumor tissue. It decreased apoptosis of CD8+ tumor infiltrating lymphocytes (TILs), and also shifts the phenotype of CD8+ TILs expressing exhaustion markers (especially PD1 negative Tim3 positive) from central memory T cells (TCM, inactive against tumor cells) to effector memory T cells (TEM, active against tumor cells). The increase in TEM cell population has been found to correlate with regression of tumor cells ⁶. In a study evaluating an experimental cancer vaccine, administration of metformin after vaccination in animal models showed an increase in CD8+ memory T cells which conferred protective immunity upon subsequent tumor challenge ⁷. Figure 1 summarizes the effects of metformin on various cellular pathways.

We have further explored the immune modulatory function of metformin. We have confirmed the positive effect of metformin on cytotoxic CD8+ T cells. Moreover, we also demonstrated for the first time that metformin inhibits regulatory T cells (Tregs) (unpublished data).

1.3 Rationale for the Current Study

1.3.1 Generating synergy and overcoming resistance to PD-1/PD-L1 inhibitors with the combination of nivolumab and metformin:

Building upon the above scientific and clinical rationale supporting the use for metformin to maximize the benefit of immunotherapy and the high unmet need for more effective treatment options for patients with non-small cell lung cancer both with and without prior exposure to PD-1/PD-L1 inhibitors, we propose a proof-of-concept parallel phase 2 trial using the combination regimen of nivolumab and metformin.

We hypothesize that the combination of nivolumab and metformin will be synergistic in effect and also will overcome the resistance to single agent PD-1/PD-L1 inhibitors. The fact that metformin activates CD8+ TILs, aids in formulation of TEMs and suppress Tregs at the same suggests that the combination of metformin and anti-PD1 monoclonal antibody, nivolumab may exert more robust immune modulatory anti-cancer effect than single agent PD-1/PD-L1 inhibitors. In addition, non-immune anti-tumor property of metformin may have assist in providing additive anti-cancer effect.

In Group B, this trial will enroll both patients who initially responded to PD-1/PD-L1 inhibitors and progressed later on as well as patients had primary refractoriness to such agents. This trial will also serve as a proof of concept trial to later further explore the effectiveness of the metformin- immune check-point inhibition combination regimen in cancers that harbor primary or secondary resistance to PD-1/PD-L1 inhibitors.

Given that the indications for PD-1/PD-L1 inhibitors in solid cancers will only expand in the near future, time is right for this proof-of-concept trial that will answer the important clinical questions in both increasing efficacy and overcoming the resistance in PD-1/PD-L1 inhibitors. This trial may pave way for the next pivotal phase 3 trial in non-small cell lung cancer or for proof of concept phase 2 trial in other cancer types where the combination treatment may be of significant clinical value.

1.3.2 Rationale for the Study Design:

NU Study Number: NU 16L04
Other Study Number: CA 209-801

Group A and Group B will address two clinical questions. Group A is designed to assess possible synergistic effect of the combination treatment in immunotherapy naïve patients whereas group B is designed to determine whether the combination treatment of metformin with immunotherapy can overcome resistance to single agent PD-1/PD-L1 inhibitors.

Group A: In order to demonstrate synergy in anti-tumor effect, ORR of the combination treatment will be compared to that of historical control (20%) reported in phase 3 single agent nivolumab trials in lung cancer (CheckMate057 and CheckMate017). Optimal Simon's two stage design will be used with target ORR of 40% versus control ORR of 20% (type 1 error rate of 0.1 and power of 0.8)

Group B: In order to find signal in patients with prior exposure to single agent PD-1/PD-L1 inhibitors, ORR of the combination treatment will be described. Optimal Simon's two stage design will be used with target ORR of 20% versus control ORR of 5% (type 1 error rate of 0.1 and power of 0.8).

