10.2 Sample Size and Accrual

Up to 49 patients (Arm A=24, Arm B=25) will be entered into the trial based on optimal Simon two stage design as below.

Arm A: In the first stage, 9 patients will be entered. If no patients show a response, then the trial will be terminated due to inactivity of the treatment. If 1 or more of 9 show a response, then an additional 15 patients will be added. If 2 or fewer of 24 show a response, then the trial will conclude that the response rate could be as low as 5%. If 3 or more respond, then the trial will conclude that the response rate is at least 20%. This design has a 20% chance of falsely concluding the rate is 5% (false negative Type II error rate = 20%, or power = 80%), and a 10% chance of falsely concluding that the rate is 20% (false positive Type I error rate = 10%). There is a 63% probability of early termination of the trial when the true response rate is 5%.

Arm B: In the first stage, 12 patients will be entered. If 2 or less patients show a response, then the trial will be terminated due to inactivity of the treatment. If 3 or more of 12 show a response, then an additional 13 patients will be added. If 7 or fewer of 25 show a response, then the trial will conclude that the response rate could be as low as 20%. If 8 or more respond, then the trial will conclude that the response rate is at least 40%. This design has a 20% chance of falsely concluding the rate is 20% (false negative Type II error rate = 20%, or power = 80%), and a 10% chance of falsely concluding that the rate is 40% (false positive Type I error rate = 10%). There is a 56% probability of early termination of the trial when the true response rate is 5%.

Due to inevaluable patients and dropout, target accrual will be 51 patients. It is anticipated that 2 patients will be accrued per month so that accrual to this study will take 2 years.

Thus, this study will be a single institution trial with duration of enrollment being 2 years. The study will be done via both internal and external referral system. Being one of the busiest lung cancer programs in the area with good advertisement plan towards partnering institutions on this clinical trial, the above accrual plan is deemed to be a feasible one.

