10.3 Data Analyses Plans

Summary of Analytic plan for primary objective	Summary of Analytic plan for secondary objectives

Please refer to the below sample size justification for the parallel Simon's two stage design which defines how the endpoints are met.
 
For Group A. Estimated ORR for historical control is 20% versus target ORR of 40% for nivolumab and metformin combination treatment.
	
Depth of response: waterfall plot Duration and persistence of response: swimmer's plot PFS: PFS at 1 and 2 years (Kaplan-Meier analysis) OS: OS at 1 and 2 years (Kaplan-Meier analysis) ORR, DCR by irRC (descriptive statistics,

NU Study Number: NU 16L04
Other Study Number: CA 209-801

For Group B. Estimated ORR for refractory patients is 5% versus target ORR of 40% for niovulomab and metformin combination treatment.
	
exact binomial confidence intervals) We will use descriptive statistics and graphical displays to evaluate change in serum biomarkers between pre- and post-treatment. A Wilcoxon signed rank test will be used to determine if there is a statistically significant change in serum biomarkers. Toxicities will be tabulated by type and grade.

--	---

The primary analysis will be on the evaluable analysis set, including all evaluable patients regardless of drug exposure. Clinical benefit rate will be defined as stable disease (for ≥ 12 weeks), complete or partial response by both the Response Evaluation Criteria in Solid Tumors (RECIST) and irRECIST. Maximum response prior to disease progression will be used. The overall response rate will be estimated by the proportion of overall response, and its 80% confidence interval (CI) and 95% CI will be estimated using the exact binomial distribution.

Additionally, we will evaluate overall response rate, defined as complete or partial response using RECIST guidelines in a similar manner. We will also perform similar analyses using Immune Related RECIST (irRECIST). Duration of response, defined as the duration from the first documentation of clinical benefit to the first documented progressive disease or death of any cause, whichever occurs first, will also be analyzed. For patients alive and progression-free at the time of data cut off, duration of response will be censored as of the last tumor assessment date. Duration of response will only be evaluated for the subgroup of patients with a clinical benefit using the Kaplan-Meier method.

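### Section 1.3.2 says Group A will demonstrate synergy, but a comparison with the 20% single-agent nivolumab rate can show only added activity, not synergy as distinct from addition

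*Combined protocol and SAP*

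**What the plan says.** Section 1.3.1 sets out the hypothesis: "We hypothesize that the combination of nivolumab and metformin will be synergistic in effect". The same paragraph adds a second possible contribution: "non-immune anti-tumor property of metformin may have assist in providing additive anti-cancer effect".

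Section 1.3.2 links the hypothesis to a test. It gives Group A the task of assessing a possible synergistic effect in immunotherapy-naive patients and then states the method: "In order to demonstrate synergy in anti-tumor effect, ORR of the combination treatment will be compared to that of historical control (20"%). That rate is the one "reported in phase 3 single agent nivolumab trials in lung cancer". The design is an optimal Simon two-stage with "target ORR of 40% versus control ORR of 20% (type 1 error rate of 0.1 and power of 0.8"). Section 10.3 repeats the rates for Group A: "Estimated ORR for historical control is 20% versus target ORR of 40% for nivolumab and metformin combination treatment".

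Other parts of the plan claim less. The primary objective (section 2.1) is anti-tumor activity measured by objective response rate. The decision text in section 10.2 draws conclusions only about the size of that rate. Neither mentions synergy.

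The documents contain no definition of synergy, no metformin-alone arm and no metformin-alone response rate. By the footnotes to Table 5-1, metformin is given alone only during the 7-day induction, and on-treatment imaging starts at Cycle 3 Day 1.

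**The concern.** Synergy means that the combination does more than the two drugs' separate effects put together. The null for that claim is the additive expectation. The null of the test in section 1.3.2 is the nivolumab-alone rate, that is, that metformin adds nothing. An additive metformin effect breaks the second null and leaves the first intact, so a positive result fits either explanation. The protocol's own rationale names addition as a possibility.

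What is at stake is the meaning of a positive Group A result. Section 1.3.2 is where the plan says what Group A is for. Read as written, it would let a response rate above 20% be described as demonstrated synergy, with an apparent 10% error rate that does not apply to that claim.

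**Working it through.** **Inputs from the documents**
- Null rate 20%, target 40%, type I error 0.10, power 0.80 (sections 1.3.2 and 10.3, Group A).
- The Simon rule that fits these rates is printed in section 10.2 under Arm B: "In the first stage, 12 patients will be entered. If 2 or less patients show a response", the arm stops; 13 more patients are added otherwise; and "If 7 or fewer of 25 show a response, then the trial will conclude that the response rate could be as low as 20"%. Success is therefore 8 or more of 25.
- The rule printed in section 10.2 under Arm A is for 5% versus 20%: stop at 0 of 9, succeed at 3 or more of 24.

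**Assumed, because the documents do not give it:** the metformin-alone response rate m, taken as 0%, 5% and 10%.

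**Step 1. Reproduce the plan's figures.** With true response rate p,

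P(success) = sum over x = 3 to 12 of P(Bin(12, p) = x) × P(Bin(13, p) ≥ 8 − x).

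At p = 0.20 the terms for x = 3, 4, 5, 6, 7 and 8 or more are 0.0234 + 0.0336 + 0.0265 + 0.0119 + 0.0031 + 0.0006 = 0.0991. At p = 0.40 the sum is 0.815. Early termination at p = 0.20 is P(Bin(12, 0.20) ≤ 2) = 0.558. A search over all two-stage designs for 20% versus 40% returns this same rule as optimal. The stated 10% error and 80% power reproduce, and the null is confirmed as a response rate of 20%.

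**Step 2. Chance of success with no synergy.** Under independent action the combination rate is p = 0.20 + m − 0.20m.

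| Assumed m | Combination rate p | P(success) | Ratio to 0.099 |
|---|---|---|---|
| 0% | 0.20 | 0.099 | 1.0 |
| 5% | 0.20 + 0.05 − 0.01 = 0.24 | 0.216 | 2.2 |
| 10% | 0.20 + 0.10 − 0.02 = 0.28 | 0.371 | 3.7 |

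If addition is instead taken as a simple sum, p is 0.25 or 0.30 and P(success) is 0.252 or 0.456.

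**Step 3. What a test of synergy would need.** Its null would sit at 0.20 + m − 0.20m, or at another stated additive expectation, and so would need a value for m. The trial cannot supply one: 7 days of metformin alone end before nivolumab starts, and no scan falls between the two.

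**Step 4. The rule printed for Arm A.** P(success) = sum over x = 1 to 9 of P(Bin(9, p) = x) × P(Bin(15, p) ≥ 3 − x). At p = 0.05 this is 0.093, matching its stated 10%. At p = 0.20, where metformin adds nothing to the historical nivolumab rate, it is 0.805.

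**The case against.** The strongest reply is that synergy is rationale language. The objective in section 2.1, the decision text in section 10.2 and the analysis plan in section 10.3 do not use the word, and section 1.3.1 glosses the hypothesis as a stronger effect than a single-agent inhibitor, which a comparison with 20% does address. Much of this stands. It limits the point to section 1.3.2 and to how the result is described. It does not remove the point, because section 1.3.2 names the inference and the test together, and section 1.3.1 uses additive as a separate term.

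A second reply is that if metformin alone produces no responses, any gain is synergy. The documents do not give that rate. Response is also a 30% cut on a continuous scale (section 6.1.7), so an additive shrinkage too small to count alone can move a stable patient across it. As an illustration, assume normally distributed tumor change with SD 25 to 45 points and 20% of patients at or below −30% on nivolumab. An additive 5-point shift then gives a success probability of 0.19 to 0.29, and 10 points gives 0.32 to 0.58. The documents specify neither this scale nor these values.

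A reader might infer three stronger things that the documents do not support:
- *That a positive Group A result will be reported as synergy.* No reporting rule says so.
- *That the follow-on trial depends on a synergy finding.* Section 1.3.1 says only that this trial may lead to one, and a gain over nivolumab of either kind would serve that purpose.
- *That the false-positive rate for synergy is some fixed multiple of 10%.* Every multiple above 1 comes from assumed metformin activity.

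**Conclusion.** The point holds, narrowly. The comparison in section 1.3.2 cannot demonstrate synergy. It can support only the statement that the combination's response rate exceeds the historical single-agent nivolumab rate. This follows from where the null sits and needs no numerical assumption.

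Its size does need one. With no synergy, the 20%/40% rule succeeds with probability 0.099 if metformin has no effect of its own, and 0.216 or 0.371 under independent action at an assumed metformin-alone rate of 5% or 10%. In each of these cases the rule fails more often than it succeeds, so an additive effect does not automatically pass; it passes more often than the nominal 10% suggests.

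These figures assume that Group A uses the rule for 20% versus 40%, as sections 1.3.2 and 10.3 imply. The study summary and section 10.2 print the 5% versus 20% rule for Arm A instead. Under that rule a combination at 20% succeeds 80.5% of the time, so even superiority to nivolumab alone would go untested. That contradiction is a separate issue, but it comes first.

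**What to change.** 1. Reconcile which Simon rule belongs to Arm A (sections 1.3.2 and 10.3 against the study summary and section 10.2). Until that is done, it is unclear what Group A tests.
2. In section 1.3.2, replace both references to synergy (the aim of Group A and the purpose of the comparison) with wording such as: *Group A tests whether the ORR of nivolumab plus metformin exceeds the historical single-agent nivolumab rate of 20%. A positive result supports added activity and does not distinguish synergistic from additive effects.*
3. Apply the same limit to the reported conclusion, in line with the objective in section 2.1.

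The hypothesis in section 1.3.1 can stay as motivation. Items 2 and 3 are edits to wording: they change no endpoint, threshold, patient number or analysis. The cost is a more modest claim.

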1.4 Nivolumab Clinical development

The U. S. Food and Drug Administration approved nivolumab (Opdivo Injection, Bristol-Myers Squibb Company) for patients with unresectable or metastatic melanoma, non-small cell lung cancer, renal cell carcinoma, and Hodgkin's lymphoma.

1.4.2 Clinical efficacy

In a phase 1 (1, 3, and 10 mg/kg nivolumab doses) dose-escalation study the 3 mg/kg dose was chosen for expanded cohorts. Among 236 patients, objective responses (ORs) (complete or partial responses [CR or PR]) were seen in NSCLC, melanoma, and RCC. ORs were observed at all doses. Median OS was 16.8 months across doses and 20.3 months at the 3 mg/kg dose. Heavily pretreated patients with NSCLC treated with nivolumab (1, 3, or 10mg/kg) achieved median OS across all dose cohorts of 9.9 months with response rates of 17% and median duration of response 17 months ⁸. In addition, responses were similar between both squamous and non-squamous carcinoma cohorts in this study. A subsequent phase 3 study compared nivolumab to docetaxel in second-line treatment setting of advanced squamous cell carcinoma among 272 patients. Nivolumab arm demonstrated superior median OS (9 vs. 6 months), 1 year survival rate (42 vs. 24%), response rates (20 vs. 9%), and significantly lower rates of grade 3-4 treatment related adverse events (7 vs. 55%) ⁹. These results supported the FDA approval of nivolumab for second-line treatment of advanced squamous cell carcinoma following treatment with platinum-based chemotherapy.

Nivolumab also has clinically meaningful activity in RCC. A phase II study treated 168 patients with advanced clear cell RCC with progression after agents targeting VEGF pathway at three doses of nivolumab (0.3, 2 and 10mg/kg) ¹⁰. Median overall survival was 18, 25, and 24 months for the three dose cohorts, respectively. More recently 821 patients previously treated with anti-angiogenic therapy were randomized to either nivolumab (3mg/Kg every 2 weeks) or everolimus (10mg daily).¹¹ The median overall survival was 25.0 months (95% confidence interval [CI], 21.8 to not estimable) with nivolumab and 19.6 months (95% CI, 17.6 to 23.1) with everolimus. The hazard ratio for death with nivolumab versus everolimus was 0.73 (98.5% CI, 0.57 to 0.93; P=0.002), which met the prespecified criterion for superiority (P≤0.0148). Response rates were in average 20% with only 11% incidence of grade 3-4 treatment-related adverse events.

NU Study Number: NU 16L04
Other Study Number: CA 209-801

1.4.3 Clinical Safety

For nivolumab monotherapy, the safety profile is similar across tumor types (investigator brochure v 2015). The only exception is pulmonary inflammation adverse events (AEs), which may be numerically greater in subjects with NSCLC, because in some cases, it can be difficult to distinguish between nivolumab-related and unrelated causes of pulmonary symptoms and radiographic changes. There is no pattern in the incidence, severity, or causality of AEs to nivolumab dose level. Safety data for subjects with previously treated advanced or metastatic NSCLC treated with nivolumab monotherapy in CA209017 (131 subjects), CA209057 (287 subjects), and CA209063 (117 subjects) were pooled and safety analyses were performed for these pooled subjects who receiving nivolumab monotherapy (a total of 535 subjects)(investigator brochure v 2015). Based on the pooled analyses, nivolumab monotherapy at a dose of 3 mg/kg administered IV Q2W has an acceptable safety profile, as demonstrated by the frequency, severity, and types of AEs, drug-related deaths, SAEs, and AEs leading to discontinuation. The most common adverse events were fatigue (19.6%), decreased appetite (12.3%), nausea (12.0%), and asthenia (10.5%). The majority of drug-related AEs were of Grade 1-2 in severity.

1.4.4 Nivolumab dosing and rationale for the flat dosing

Anti-tumor activity was observed in study CA209003 at dose levels ranging from 1 to 10 mg/kg in RCC. The antitumor activity of nivolumab tended to increase with dose, as did the incidence of SAEs. The anti-tumor activity of nivolumab in RCC was investigated at dose levels 1 and 10 mg/kg, with the higher activity observed at 10 mg/kg. The observed anti-tumor activity in melanoma, and NSCLC was highest at 3 mg/kg, suggesting that anti-tumor activity approaches a plateau at dose levels of 3 mg/kg and above. Consistent with these observations, the results of the exposure-response analyses for these tumor types, show that the probability of a tumor response tended to approach a plateau for trough concentrations produced by 3 and 10 mg/kg every 2 week dosing. Nivolumab was adequately tolerated up to 10 mg/kg, the highest dose level tested, and no maximum tolerated dose (MTD) was identified. Although the spectrum, frequency, and severity of nivolumab-related AEs were generally similar across the dose levels tested, the 10 mg/kg doses level had numerically higher Grade 3/4 drug-related SAEs and AEs leading to discontinuation. Based on the totality of the safety, efficacy, and exposure-response data, a dose of 3 mg/kg every two weeks was selected as the dose anticipated achieving an appropriate balance of benefit and risk.

